1.4 HOPE Peru: Women helping women fight cervical cancer

Based on the success of HOPE, we applied for additional funding to continue improving this model. In hopes of securing sustainability, we proposed the creation of the first Peruvian public health social enterprise aiming to improve access to healthcare technologies for communities with the involvement of women from the communities. HOPE's first project seeks to market the HPV self-testing (CareHPV®), to gain commitment, and to promote a culture of cervical cancer prevention. The tests will be sold to high-income women to create a sustainable platform to offer free testing to women with

less resources involving training of community women (as the "HOPE Ladies"). The project is based on four key pillars: (1) the use of molecular HPV tests for screening, with better sensitivity and affordability than PAP tests; (2) the use of self-collected vaginal samples, which offers an opportunity to increase screening coverage; (3) community women teaching other women about cervical cancer and how to apply the HPV self-test; and (4) use of affordable technology and development of an informatics platform to collect data for the distribution of molecular HPV screening tests, results, follow-up of women screened, and the transmission of reminders through text messages (SMS) for clinic visits, along with an internet information platform and hot-line. Additionally, HOPE is promoting the concepts of timely detection and saving another life through the purchase of a kit, since for each test sold, we will be able to reach a woman who otherwise would not likely be tested for cervical cancer.

The distribution model relies on "HOPE Ladies", women from marginalized communities who disseminate information on HPV door-to-door in their communities, and then provide screening kits for convenient and relatively comfortable self-testing for free or at a semisubsidized price, depending on the region. The HOPE Ladies receive an incentive for every test distributed. This project is in the phase of transition to scale and has received funding for Grand Challenges Canada for up to 1 million CAD for the next three years, for which it required matching funding. So far, HOPE has received funds from Fogarty NIH, the Center for Global Health, the University of Manitoba, Crowdfunding, United for Health Innovation (UfHI), Global Coalition Against Cancer, and Qiagen.

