In recent years the global attention turned to thermal-coagulation, an electricity-powered device used for 50 years in United Kingdom and some countries in Asia; the cure rates of thermal ablation in those settings is around 90%, better than cryotherapy, and comparable to LEEP. In addition, the thermal ablation units can be powered with rechargeable batteries similar to cell phones, and very light for transportation (1 Kg) and they do not need any supplies to work. In May 2019 the WHO approved the new guidelines for use of thermal ablation, recommending thermal ablation for the treatment of pre-cancerous lesions of the uterine cervix.

II. AIMS

The continuum of care is one of the main challenges to ensure effective actions against cervical cancer. We are proposing to leverage what we are doing within the project "HOPE Peru: Women helping women fight cervical cancer" and improving treatment at the health center for those women found to be HPV(+). Our goal is to demonstrate that the combination of HPV self-sampling with the participation of community women, the Pocket colposcope and the thermocoagulator will yield a high proportion of HPV positive women who complete treatment and follow-up care.

Main Aim

To perform a demonstration trial on the feasibility of HPV self-sampling as a way to mobilize women to get to the next level of care and the feasibility of a "see and treat" strategy in a community health setting and the effectiveness of the Pocket colposcope and the thermocoagulator to improve the rates of treatment and follow up care to women who have a positive HPV results.

Specific Aims

Aim # 1: To assess the proportion of HPV positive women who go to a health center for treatment, are examined with the Pocket Colposcope and if required, received Thermocoagulation.

Aim # 2: To assess the proportion of HPV positive women that receive treatment and a 6 month follow up visit.

Aim #3: To evaluate feasibility, acceptability, and ease of use of the Pocket colposcope Aim #4: To assess the costs, cost-effectiveness, and population health impact of using the pocket Colposcope, and thermocoagulator for cervical cancer treatment.

III. LOGIC MODEL AND FRAMEWORK

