In this study, the construct of the continuum of care will be applied for the evaluation of losses within the process of linkage to treatment after a woman receives a positive results from HPV screening until she receives her treatment and has her six month follow-up visit. We will also include the addition of the time required for transitions from one step to the next, and we will track cases to analyze causes of loss within the care cascade, as done in other settings²⁴.

IV. METHODOLOGY

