4.3 Study population and sample size

Our main aim is to increase the proportion of women HPV(+) who complete treatment. From previous data collected in the region of Callao, we have found that only around 30% of women found to have an abnormal high-grade PAP completed treatment in 2014, we will explore if there is data available in Cajamarca to calculate comparative historical information regarding rates of treatment of women with positive screening tests.

Power Calculations: With an overall testing population of 10,000 women, assuming 10% HPV positivity, there will be approximately 1,000 HPV positive women. Assuming an uptake rate of 80%, the effective sample size will be 800 HPV(+) women for follow. This will provide us with a precision of 3.5% or better for the estimation of the proportions to be estimated in the two primary outcomes²⁷. We are planning to include 10 to 12 health centers in the region, with around 60-80 women HPV(+) to be seen and followed in each center.

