4.5 Data collection

Part of the data will be collected directly on the HOPE informatics platform: system in β version currently in use for the collection of data of logistics of the HPV test distribution, processing, and results. As part of the project we will develop fields for the follow-up of each woman so we will be able to collect the specific data on times. The data for follow-up will be collected directly from the medical records.

For the surveys and qualitative data collection, data will be collected and analyzed accordingly.

Costing data will be collected as part of the baseline data collection and during the implementation. At the end a costing evaluation and cost-effectiveness analysis will be performed

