5.2.5 Adaptation/Enhancement of the HOPE platform

We will assure that the indicators pertinent to the project will be captured. We will also develop a module for follow up of the cases.

5.2.6 Development of training manuals, videos and other materials for providers who will use the pocket colposcope and the thermocoagulator. These materials should be easily accessible for providers in low-resource clinics.

5.3 Implementation of the local laboratory in Cajamarca for the processing of the HPV tests.

The staff of the DIRESA laboratory will be trained in the processing of HPV tests. We will provide the necessary equipment, implement a quality control system, and set up a connection to the HOPE digital platform.

5.4 Designation of health centers to participate in the trial and training of health providers at Health Centers (intervention and control)

Providers will need to be trained about the study protocol, the national guidelines for cervical cancer, the use of the thermocoagulator, visual counseling, and pocket, and the deployment of equipment.

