5.9 Process and Impact Measures

in the Andean Region where we will be working		
Implementation of local laboratory with capabilities to process HPV testing	1 laboratory implemented for HPV testing	Visit Report
Identification of rural health clinics in Andean region of Peru and provision of appropriate equipment (pocket colposcope, thermocoagulators)	 # of health clinics (10-12) # of innovations deployed # thermocoagulators deployed (#10-12) # pocket colposcopes deployed (10-12) 	Visit reports
Send staff to train HOPE Ladies in the rural regions chosen	# HOPE Ladies trained and registered	HOPE informatics platform
Preparation of tools for the use of pocket colposcope and thermocoagulator	manual of use of pocket colposcope and thermocoagulator finished in Spanish. Video tutorial for the use of pocket colposcope	Reports Tools ready
Send staff to train health providers in the use of pocket colposcope and thermocoagulators	 # of health providers trained on the use of pocket colposcope # of health providers using pocket colposcope # of providers using thermocoagulator 	Reports
Provide 10,000 HPV self- sampling kits for HOPE ladies to distribute	 # of HPV tests distributed to HOPE ladies # of HPV tests correctly returned # of HPV tests processed # of HPV tests positive # of women who receive HPV positive results 	HOPE informatics platform

Facilitate women HPV (+) to get treatment at Health centers	% of HPV (+) women coming to the health center for treatment	Monitors/hope ladies HOPE informatics platform
Health centers giving treatment and F/U to HPV (+) women	-% of HPV (+) women completing treatment -% of HPV (+) women completing F/U at 6m	Monitors/ review health centers records (check list) HOPE informatics platform
Conduct a post-study evaluation (qualitative, quantitative) of providers to evaluate acceptability and ease of use (pocket colposcope)	# of providers who indicate they would use the Pocket/thermocoagulator regularly for cervical cancer diagnosis/treatment or found it useful	Report of results
Measuring Efficiency	-Average time to come for treatment -Average time to complete treatment	Monitors/ review health centers records (check list) HOPE informatics platform
Cost-effectiveness	Complete cost of care cascade Patient level cost Monthly budget Cash on hand Co-funder contribution Personel	Report

*PC + TC = Pocket Colposcopy + Thermocoagulator

VI. ETHICAL CONSIDERATIONS

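### The efficiency averages cover only women who reach each step, so they do not describe delay across all HPV-positive women; cumulative incidence over the whole group would, at little cost.

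*Combined protocol and SAP*

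**What the plan says.** The efficiency row of the table in section 5.9 names two metrics and nothing more: "Average time to come for treatment -Average time to complete treatment". It gives no denominator and no rule for women who have not reached the step. The same table lists, as separate indicators, the percentages of HPV-positive women who attend, complete treatment and complete the 6-month follow-up.

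Section III (Logic model and framework) explains what the times are for. The continuum of care is used to study losses from receipt of a positive result through treatment to the 6-month visit, and "We will also include the addition of the time required for transitions from one step to the next". So the framework does set a starting point, although the row in 5.9 does not repeat it.

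Section 4.3 expects about 1,000 HPV-positive women and continues: "Assuming an uptake rate of 80%, the effective sample size will be 800 HPV(+) women for follow". Under Aim 1 (section II), women who attend "are examined with the Pocket Colposcope and if required, received Thermocoagulation", so not every attender is treated. Section 5.7 records dates, procedures and their results for HPV-positive women who come to a center, and plans descriptive analysis. No censoring or cumulative-incidence method is named.

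On data sources, section 4.5 describes the HOPE platform as "currently in use for the collection of data of logistics of the HPV test distribution, processing, and results" and adds that fields for each woman's follow-up will be built to capture times. Section 5.2.5 says "We will also develop a module for follow up of the cases". Section 5.9 also counts the number "of women who receive HPV positive results".

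**The concern.** An average time to an event can be taken only over women who had the event. Here three kinds of women fall outside it: those who never come, those who would come but have not done so by data close, and, for the treatment metric, those examined and found to need no treatment. The first two are part of the delay problem that the cascade is meant to show. The third group is not a loss at all, but in an average of treatment times it is absent in the same way as women who were lost.

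What is at stake is interpretation. A mean of about a month to attendance reads as the speed of the programme, yet the same mean can arise whether 80% or 50% of HPV-positive women ever attend. The percentages alongside tell the reader how many are missing but carry no timing, and they do not undo the cut-off of late attenders.

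**Working it through.** **1. Women outside the average.** Inputs from section 4.3: 10,000 tested, 10% positive, 80% uptake.

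- HPV-positive: 10,000 × 0.10 = 1,000. Followed: 1,000 × 0.80 = 800. Both reproduce the plan's figures.
- Without a time to attendance: 1,000 − 800 = 200, or 20%.
- The timeline (section VII) lists 2,400 HPV-positive women instead. On that count, 0.20 × 2,400 = 480; the share is the same.

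The plan gives no figure for either average, so everything below is illustration with assumed inputs.

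**2. The average does not respond to the share attending.** Assume a proportion π ever attends, with exponential delay of mean μ = 3 months among those women. With complete follow-up the planned average is 3 months whatever π is. Over all HPV-positive women:

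- proportion attended by time t: π(1 − exp(−t/μ)). At 90 days (90/30.44 = 2.957 months), 1 − exp(−2.957/3) = 0.627.
- median: −μ ln(1 − 0.5/π), if π > 0.5.

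| π | Planned average (months) | Attended by 90 days, all women | Median, all women (months) |
|---|---|---|---|
| 0.8 | 3.0 | 0.8 × 0.627 = 0.50 | 2.94 |
| 0.6 | 3.0 | 0.6 × 0.627 = 0.38 | 5.38 |
| 0.5 | 3.0 | 0.5 × 0.627 = 0.31 | not reached |

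The gap is not always large. With μ = 1 month and π = 0.8 the all-women median is −ln(0.375) = 0.98 months, against an average of 1.00.

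**3. Late attenders cut off at data close.** Assume entry spread evenly over 12 months and close at month 18, so follow-up C is uniform on 6 to 18 months and every woman has time for the planned 6-month visit. The reported mean is

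E[T | T < C] = {μ(1 − A) − B} / (1 − A), where

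- A = mean of exp(−C/μ) = μ(e^(−6/μ) − e^(−18/μ))/12
- B = mean of C·exp(−C/μ) = μ{(6 + μ)e^(−6/μ) − (18 + μ)e^(−18/μ)}/12

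For μ = 3: A = 0.0332, B = 0.2915, so the reported mean is (3 × 0.9668 − 0.2915)/0.9668 = 2.70.

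| True mean among eventual attenders (months) | Reported mean, close at month 18 | Shortfall |
|---|---|---|
| 1 | 1.00 | 0.1% |
| 2 | 1.93 | 3.3% |
| 3 | 2.70 | 10.1% |
| 6 | 4.09 | 31.9% |

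A later close shrinks this: at month 21 a true mean of 3 months is reported as 2.85.

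**4. Does the alternative recover the truth?** In 1,000 simulated studies of 1,000 HPV-positive women (80% ever attending, mean delay 3 months, 12-month entry, a deliberately early close at month 15, 30% of attenders needing no treatment; all assumed), the Aalen-Johansen estimates by 30, 90 and 180 days were 0.225, 0.502 and 0.688 for attendance (true 0.224, 0.501, 0.689) and 0.158, 0.351 and 0.481 for treatment (true 0.157, 0.351, 0.482). The simple average in the same data was 2.42 months against a true 3. For simplicity the simulation dated treatment at attendance, so it does not test a separate interval from attendance to completed treatment.

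**The case against.** The best defence is that the plan never says these averages describe all HPV-positive women. Section III asks for transition times between steps, and a transition time exists only for women who make the transition. A proportion reaching each step, plus a mean time among those who did, is an ordinary two-part description; both parts are in the same table, and cases are tracked for causes of loss. Women needing no treatment rightly have no treatment time, and section 5.7 already collects the results that identify them. Much of this stands. The simple average is legitimate if it is labelled. What it cannot do is place timing in the full cascade, which is the use section III gives it, and no rule covers women without the event.

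Four stronger readings are tempting, and the documents do not support them.

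- *That the time origin is missing.* Section III starts the window when a woman receives a positive result. The row in 5.9 merely fails to adopt it.
- *That truncation is severe.* That needs long delays or an early close. A close at month 15 would report a true mean of 3 months as 2.43, but it leaves the last entrants 3 months of follow-up, too little for the planned 6-month visit.
- *That the metric will mislead a comparison of reminders.* Section 1.4 describes "the transmission of reminders through text messages (SMS) for clinic visits" as part of the platform. If 700 women average 1 month and reminders bring in 100 more averaging 5 months, the mean rises to (700 × 1 + 100 × 5)/800 = 1.5 months although more women are seen. But no comparison with and without reminders is planned, and the higher attendance would show in the same table.
- *That every result date is already held.* The platform handles results, and the table counts women who receive them, but neither confirms a date for each HPV-positive woman.

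**Conclusion.** The point holds as a minor one. The planned averages leave out about 20% of HPV-positive women at the plan's own uptake assumption, and do not describe delay across the group the cascade follows. That conclusion needs no assumption beyond the 80%.

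The further shortfall from late attenders cannot be sized from the documents, which give neither delays nor a readable closing date. Under exponential delays, 12-month entry and a close at month 18, it is under 4% for true means up to 2 months, about 10% at 3 months and about 32% at 6 months. If women come within about a month it is negligible.

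A reader might infer that the trial's main result is at risk. It is not: these are process indicators, and the primary proportions and their sample size are untouched. Nor should one expect the revised figure always to look worse than the average, as the comparison of 0.98 with 1.00 months shows.

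**What to change.** - State in section 5.9 that time runs from the date the woman received her positive result, matching section III. If receipt is not recorded, use the result date. First confirm that the platform holds the chosen date for every HPV-positive woman, not only for those who reach a center.
- For attendance, report the cumulative incidence over all HPV-positive women, censored at data close, with proportions by 30, 90 and 180 days and the median if it is reached.
- For treatment, report cumulative incidence (Aalen-Johansen) with examined, no treatment required as a separate competing outcome, coded from the procedure results already collected under section 5.7. These women are then not counted as untreated.
- Keep the simple averages if wanted, labelled as among women who reached the step, with n.

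The cost is one date field to confirm, one outcome code and slightly more analysis. No change to the sample size, the visits or the primary outcomes is needed.
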